4.0 Analysis Populations

The intent-to-treat (ITT) Population, which includes all randomized subjects, will be used for all efficacy analyses. Subjects who are randomized to placebo in Period A and do not

continue into Period B will be excluded from the analysis in Period B. Subjects will be analyzed according to treatment as randomized.

The Per-Protocol (PP) Population will include ITT subjects who meet all the following criteria:

[figure not shown]
- Receive at least 75% of the planned study drug prior to Week 16.
- Provide at least one post Baseline assessment on lesion count.
- Have Baseline AN count ≥ 5 .
- Have Baseline draining fistula count ≤ 20 .
- Do not take protocol prohibited medications that could potentially impact the efficacy assessment for the primary endpoint at Week 16.

The final criteria and the exclusion of subjects from the PP Population will be finalized before unblinding data for the Primary Analysis. Subjects in the PP population will be analyzed by treatment group as randomized.

The following populations will be used for the safety analysis:

- The Safety Population in Period A (Safety_A) is defined as all subjects who are randomized and received at least one dose of study drug in Period A.
- The Safety Population in Period B (Safety_B) is defined as all subjects who received at least one dose of study drug in Period B.
- The All Risankizumab Treated (ALL_RZB) Population is defined as subjects who received at least one dose of risankizumab in the study. This population will be used to provide a comprehensive summary of safety.

For safety analysis, subjects will be analyzed as treated (determined by the first dose of study drug that the subject received).

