9.1 General Considerations

All efficacy analyses will be conducted in the ITT Population. In addition, Per-protocol analysis for primary endpoint will be performed. All statistical tests, between each risankizumab dose and placebo, will be performed at a two-sided alpha level of 0.025.

The Primary Analysis will be performed after the last ongoing subject has completed the Week 16 visit, and the data up to Week 16 have be cleaned. This will be the only and final analysis for the primary and ranked secondary endpoints. Study sites and subjects will remain blinded to their initial treatment assignment for the duration of the entire study.

For categorical endpoints, comparisons will be made between each risankizumab dosing group and placebo using the Cochran-Mantel-Haenszel (CMH) test, adjusting for the actual values of stratification factors. In case of any stratum with zero subject in either treatment group, no stratification factor will be controlled. Non-responder imputation (NRI) will be the primary approach to handle missing values. To account for the impact of COVID-19 pandemic, the NRI will be adjusted to NRI-C, Non-Responder Imputation incorporating multiple imputation to handle missing data due to COVID-19.

For continuous endpoints, comparisons will be made between each risankizumab dosing group and placebo based on the fixed term of treatment from a Mixed-effect Model

[figure not shown]
Repeat Measurement (MMRM) model including the Baseline value and observed measurements at all post-baseline visits, adjusting for the fixed effects of treatment, actual values of stratification factors, visit and treatment-by-visit interaction as covariates. The MMRM will be the primary approach to handle missing values.

For variables other than PGA Skin Pain NRS and HSSA, "Baseline" refers to the last non-missing observation on or before the date of the first administration of study drug or the date of randomization if no study drug is given. The "Baseline" of PGA Skin Pain NRS and HSSA is defined as the last non-missing weekly average score, calculated based on the daily scores from the past 7 days, on or before the date of the first administration of study drug or the date of randomization if no study drug is given. For variables where the assessment time is collected on the ePRO device, the baseline measurement must be prior to the time of the first administration of study drug.

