10.0 Safety Analyses

10.1 General Considerations

Safety analyses will include adverse events, laboratory, and vital sign measurements.

Safety data will be summarized among the Safety_A and Safety_B populations by treatment groups. For the safety analysis, subjects are analyzed based on the actual treatment group, determined by the first dose of study drug that the subject received.

The overview of TEAEs, areas of safety interest (ASIs), and potentially clinically important (PCI) findings in laboratory variables and vital sign variables will be summarized among the ALL_RZB Population.

Missing safety data will not be imputed.

[figure not shown]

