10.3 Analysis of Laboratory Data

Data collected from central and local laboratories, including additional laboratory testing due to an SAE, will be used in all analyses, except for Baseline derivation where SAE-triggered laboratory assessments on or before the first dose of study drug will be excluded. The clinical laboratory tests defined in the protocol operations manual (e.g., hematology and clinical chemistry) will be summarized.

Mean change from Baseline to each applicable post-baseline visit will be summarized for selected laboratory variables. The following descriptive statistics will be presented by treatment groups: number of observations, Baseline mean, visit mean, mean change from Baseline and its standard error, and the 95% confidence interval of the mean change from Baseline.

[figure not shown]
In addition, laboratory parameters will be tabulated using shift tables from Baseline to minimum and maximum values in each period (Period A and Period B), categorized by the toxicity grade according to NCI CTCAE Version 4.03¹ of the laboratory used for each sample. A similar shift table will also be provided to summarize shifts from Baseline to the final post-baseline value in each period.

Laboratory abnormalities meeting CTC criteria grade 3 and 4 at least once in each period will be summarized.

Laboratory abnormalities will be evaluated based on Potentially Clinically Important (PCI) criteria (Appendix C). For each laboratory PCI criterion, the number and percentage of subjects who have a laboratory value meeting the criteria at least once in each period will be summarized. Listings will be provided to summarize subject-level laboratory data for subjects meeting PCI criteria.

In addition, the frequencies and percentages of subjects with post baseline liver specific function test values in ALT/SGPT, AST/SGOT, alkaline phosphatase, and total bilirubin that meet the following criteria will be summarized by treatment groups:

- ALT $\geq 3.0 \times ULN$
- ALT $\geq 5.0 \times ULN$
- ALT $\geq 10.0 \times ULN$
- ALT $\geq 20.0 \times ULN$
- AST $\geq 3.0 \times ULN$
- AST $\geq 5.0 \times ULN$
- AST $\geq 10.0 \times ULN$
- AST $\geq 20.0 \times ULN$
- Alkaline phosphatase $\geq 1.5 \times ULN$
- Total bilirubin $\geq 2.0 \times ULN$
- ALT and/or AST $> 3 \times$ ULN and TBL $\geq 2 \times$ ULN

A listing of potentially clinically important (PCI) liver function laboratory values will include all subjects who met any of the following four criteria:

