Appendix C. Potentially Clinically Important Criteria for Safety Endpoints

The criteria for Potentially Clinically Important (PCI) laboratory findings are described in Table C-1 and Table C-2.

Table C-1. Criteria for Potentially Clinically Important Hematology Values

[figure not shown]
		Definition of Potentially Clinically Important: NCI CTCAE (Version 4) Grade 3 or Greater
Hematology Variables	Units	Very Low
Hemoglobin	g/dL	< 8.0
Platelets count	$10^{9}/L$	< 50.0
WBC count	$10^{9}/L$	< 2.0
Neutrophils	10 ⁹ /L	< 1.0
Lymphocytes	10 ⁹ /L	< 0.5

Note: A post-baseline grade must be more extreme than the baseline grade to be considered a potentially clinically important finding.

Table C-2. Criteria for Potentially Clinically Important Chemistry Values

[figure not shown]
		Definition of Potentially Clinically Important: NCI CTCAE (Version 4) Grade 3 or Greater	
Chemistry Variables	Units	Very Low	Very High
TBL	mcmol/L		> 3.0 × ULN
ALP	U/L		$> 5.0 \times ULN$
SGOT/AST	U/L		$> 5.0 \times ULN$
SGPT/ALT	U/L		$> 5.0 \times ULN$
Albumin	g/L	< 20	
Glucose	mmol/L	< 2.2	> 13.9
Triglycerides	mmol/L		> 5.7
Creatinine	mcmol/L		$>$ 3.0 \times ULN or $>$ 3.0 \times baseline
Sodium	mmol/L	< 130	> 155
Potassium	mmol/L	< 3.0	> 6.0
Calcium	mmol/L	< 1.75	> 3.1
CPK	U/L		$> 5.0 \times ULN$
Total Cholesterol	mmol/L		> 10.34
GGT			> 5.0 × ULN

Note: A post-baseline grade must be more extreme than the baseline grade to be considered a potentially clinically important finding.

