Appendix D. Criteria for Potentially Clinically Important Vital Sign Values

Vital Signs Variables	Criterion	Definition of Potentially Clinically Important
Systolic Blood	Low	Value ≤ 90 mmHg and decrease ≥ 20 mmHg from Baseline
Pressure (mmHg)	High	Value ≥ 160 mmHg and increase ≥ 20 mmHg from Baseline
Diastolic Blood	Low	Value ≤ 50 mmHg and decrease ≥ 10 mmHg from Baseline
Pressure (mmHg)	High	Value ≥ 100 mmHg and increase ≥ 10 mmHg from Baseline

Appendix E. Non-Responder Imputation Incorporating Multiple Imputation to Handle Missing Data Due to COVID-19 Pandemic for Dichotomized Outcome Variables

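### In ALL_RZB, laboratory and blood-pressure PCI findings are judged against the Week 0 Baseline, although placebo-randomized subjects first receive risankizumab at Week 16.

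*SAP*

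**What the plan says.** SAP 9.1 gives the only general definition of Baseline: it "refers to the last non-missing observation on or before the date of the first administration of study drug", or the randomization date if no drug was given. SAP 10.3 uses the same anchor for laboratory data, with one exclusion: "SAE-triggered laboratory assessments on or before the first dose of study drug will be excluded". Neither section defines a Baseline for Period B or for first exposure to risankizumab.

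SAP 10.1 states that PCI "findings in laboratory variables and vital sign variables will be summarized among the ALL_RZB Population". Both sets of PCI criteria refer to Baseline:

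- Laboratory (Appendix C) requires CTCAE grade 3 or greater and adds: "A post-baseline grade must be more extreme than the baseline grade to be considered a potentially clinically important finding".
- Blood pressure (Appendix D) combines a threshold with a change. The rule for high systolic pressure is "Value ≥ 160 mmHg and increase ≥ 20 mmHg from Baseline".

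Under SAP 4.0, ALL_RZB contains everyone with at least one risankizumab dose. That includes placebo-randomized subjects who start risankizumab 360 mg at Week 16 (SAP 2.2).

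**The concern.** ALL_RZB is intended as the comprehensive safety summary for risankizumab. For a subject who crosses over from placebo, the reference value in that summary precedes first exposure by 16 weeks. A placebo-period change that persists or is measured again after Week 16 meets the rule and is reported as a finding on risankizumab. The reverse also happens: if the Week 0 value was abnormal, the value had recovered by Week 16 and it became abnormal again on risankizumab, the rule does not count it. A reader of the table could not tell either case from a finding that arose on the drug.

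**Working it through.** The plan states no rate or count for these findings, so there is no figure to reproduce. The check traces the definitions, applies a PCI rule under both anchors, and bounds the size.

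**1. Does study drug include placebo?** Yes. Safety_A is "all subjects who are randomized and received at least one dose of study drug in Period A", and it covers all three arms. Where the SAP means risankizumab alone it says so, as in the ALL_RZB parts of 6.0, 10.2.1 and 10.2.4. Baseline for a placebo-randomized subject is therefore Week 0.

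**2. Starting points for the same population.**

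| ALL_RZB quantity | SAP section | Reference for a placebo-randomized subject |
|---|---|---|
| Treatment duration | 6.0 | First risankizumab dose (Week 16) |
| TEAEs | 10.2.1 | First risankizumab dose (Week 16) |
| Patient-years | 10.2.4 | First risankizumab dose (Week 16) |
| PCI Baseline, laboratory and blood pressure | 9.1, 10.3, Appendices C and D | First study drug (Week 0) |

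An adverse event with onset at Week 10 on placebo is left out of ALL_RZB. A blood-pressure rise that began at Week 10 and persists is counted.

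**3. Counting window.** SAP 10.3 and 10.4 count values meeting the criteria at least once in each period. They do not say which laboratory and vital-sign values belong to ALL_RZB, so the window is open as well as the Baseline.

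**4. The systolic rule under both anchors** (illustrative values; the rule needs at least 160 mmHg and a rise of at least 20).

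| Case | Week 0 | Week 16, before risankizumab | Week 20 | Against Week 0 | Against Week 16 |
|---|---|---|---|---|---|
| Onset on placebo | 138 | 165 | 164 | 164 − 138 = +26: PCI | 164 − 165 = −1: not PCI |
| Onset on risankizumab | 165 | 135 | 165 | 165 − 165 = 0: not PCI | 165 − 135 = +30: PCI |

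The first case is a false risankizumab finding, and the second is a missed one.

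**5. Size.** Inputs: 74 subjects per arm and 222 in total (SAP 2.4, Table 1).

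- Share exposed, if every placebo subject crosses over: 74 / 222 = 33.3%.
- Subjects miscounted at an assumed 1% to 5%: 74 × 0.01 = 0.74; 74 × 0.05 = 3.70.
- As points of ALL_RZB: 0.74 / 222 = 0.33; 3.70 / 222 = 1.67.
- If only 85% cross over (also assumed): 74 × 0.85 = 62.9 subjects, and ALL_RZB is 148 + 62.9 = 210.9. The result is 0.63 to 3.15 subjects, or 0.30 to 1.49 points.

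**The case against.** **A reader might infer that the Period B shift tables and mean changes are wrong in the same way.** The documents do not support that. SAP 4.0 and 10.1 group safety subjects by the first study drug received, so in Safety_B the crossover subjects form their own group and are not pooled with the risankizumab-randomized arms. Shift tables are specified by period, and mean changes by visit and treatment group; neither is assigned to ALL_RZB. SAP 10.3 and 10.4 report visit means, and Protocol Appendix D schedules hematology, chemistry and vital signs at Week 16, so change after the switch can be read directly. Re-anchoring those tables would cost a common reference visit, which makes it a trade-off and not a correction.

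**A reader might infer that all laboratory abnormality counts are affected.** The liver multiples of ULN and the CTC grade 3 and 4 counts in SAP 10.3 are not relative to Baseline. Persisting placebo-onset values are counted there too, but a new Baseline would not change those tables.

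**A reader might infer that the primary safety objective is compromised.** That objective compares risankizumab with placebo, which is the Period A comparison, and Week 0 is the right reference there for every arm. ALL_RZB is descriptive, with no test or decision rule attached.

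**Subject-level PCI listings are planned** (SAP 10.3, 10.4). If they show values by visit, a placebo-onset case could be recognized. That helps a careful reader but does not correct the ALL_RZB count.

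**The definition sits in the efficacy section, and the product safety SAP may set another convention.** The wording of 9.1 is general, and 10.3 agrees with it. The version history says that the PCI and shift-table definitions were aligned with the product safety SAP, but this SAP does not refer to that document for Baseline. Since that document is not available here, certainty is somewhat lower.

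What stands against all of this is the PCI count in ALL_RZB.

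**Conclusion.** The point holds for laboratory and blood-pressure PCI findings in ALL_RZB, and only there. As written, the rule attributes persisting or recurring placebo-onset changes to risankizumab and can miss changes that arise on it. It also disagrees with the starting point that the SAP uses for TEAEs, duration and patient-years in the same population.

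Up to 33% of ALL_RZB is exposed to the error, if all placebo subjects cross over. The likely effect is small: 0.3 to 1.7 percentage points under the assumed 1% to 5%, a range that nothing in the documents confirms. An abnormality that resolves before Week 16 and does not return has no effect, provided that only values after first risankizumab are counted. The Period A safety comparison and all efficacy results are untouched. This is a minor correction, worth making because it is cheap and the stated rule misassigns findings.

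**What to change.** Add to SAP 10.1, for ALL_RZB PCI analyses only:

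- **Baseline** is the last non-missing value on or before the first risankizumab dose. For any Risankizumab 360 mg group, it is the last value on or before the first 360 mg dose, since subjects randomized to 180 mg first receive 360 mg at Week 20.
- **Counting window:** only values after that dose count, within the window that SAP 10.2.1 uses for ALL_RZB TEAEs (up to 140 days after the last risankizumab dose or the end of study, whichever is earlier).
- **Lipids** keep the Week 0 value. The activity schedule appears to have no Week 16 lipid sample, although that table is broken in the available text.

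Keep the Week 0 Baseline for Period A and for the by-period Period B tables.

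No new data are needed: hematology, chemistry and vital signs are already scheduled at Weeks 16 and 20. The cost is a second derived baseline flag and a footnote explaining the two references. One loss should be stated openly. Because Appendix C requires a grade worse than Baseline, a crossover subject with a transient grade 3 value at Week 16 would not be counted if the same grade recurred on risankizumab. The fixed-threshold liver and CTC grade 3 and 4 counts stay as they are.

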9.2 Handling of Missing Data

Missing data could occur due to various reasons, including missing visits/assessments, early withdrawal from the study, or missing due to COVID-19 infection or logistic restriction.

The COVID-19 pandemic is interfering with the conduct of many ongoing trials, with potential impacts on treatment duration and the collection, analysis and the interpretation of clinical trial data. Some protocol-specified visits in the clinical trials may be impacted due to COVID-19 infection or logistical restrictions during the pandemic. For example, some scheduled visits may be missed due to self-quarantine or local government restrictions on travel; some visits may also be delayed or canceled due to healthcare resource constraints during the pandemic. Impacted visits due to COVID-19 will be recorded in the database. The probability of having missed visits and missing data due to COVID-19 infection or logistical restrictions related to the COVID-19 pandemic can be reasonably assumed to be unrelated to the unobserved values. Therefore, for the purpose of statistical analysis, it is reasonable to assume that these missing data are missing at random (MAR) and the statistical models that require MAR assumption are appropriate.

Sensitivity analyses will be performed to assess the impact of missing data and the robustness of the conclusion.

Handling of missing data for the efficacy analyses is described below.

[figure not shown]
9.2.1 Categorical Endpoints

Non-Responder Imputation incorporating multiple imputation to handle missing data due to COVID-19 (NRI-C) will be the primary approach for handling missing data in the analysis of categorical endpoints.

For any categorical endpoints of achievement, the NRI-C will categorize any subject who does not have an evaluation during a pre-specified visit window as a non-responder for the visit. The only exceptions are: 1) when the subject is a responder both before and after the visit window in the particular Study Period, the subject will be categorized as a responder for the visit; 2) missing data due to COVID-19 infection or logistical restriction will be handled by MI. Subjects receiving any prohibited antibiotics for HS-related infections or discontinued study drug due to lack of efficacy will be counted as non-responders at later visits. Subjects whose change/percent change from Baseline cannot be calculated because of a missing Baseline will be considered as non-responders at all post-baseline visits. The only exception is that when determining the HiSCR response status, a subject with missing Baseline value will be counted as a non-responder at any post-baseline visit unless a subject's abscess, inflammatory nodule, and draining fistula counts are all zero at a specific visit, then the subject will be a HiSCR responder at that visit. More details are provided in Appendix E.

[figure not shown]
For any categorical endpoints that connote worsening of disease, subjects with observed worsening outcomes, including those after receiving any prohibited antibiotics for HS-related infections or discontinued study drug due to lack of efficacy, will be counted as experienced such worsening.

Of note, during the Primary Analysis upon completion of Week 16, the NRI-C analysis will only be performed at all visits up to Week 16.

Multiple Imputation (MI) will be used as a sensitivity analysis for the primary endpoint (HiSCR at Week 16). PROC MI with the Markov Chain Monte Carlo (MCMC) statement will be first applied to generate 30 augmented datasets with monotonic missing pattern. The random seed for the MCMC will be the SAS numerical value of the first subject randomization date. PROC MI will then be used to impute 30 complete datasets using the regression method. The random seed for this imputation step will be the SAS numerical value of the last subject randomization date. Taking abscess count as an example, the variables to be included in the imputation model are: treatment group, prior exposure to anti-TNF category, Baseline worst Hurley Stage, Baseline abscess count, and abscess counts at each visit up to the end of the double blind Period A. The imputed post-baseline abscess counts will be rounded to the same precision as the observed data to determine the responder status. The same imputation strategy will be applied to the inflammatory nodule count and the draining fistula count. HiSCR status will be determined accordingly. Using the Cochran-Mantel-Haenszel (CMH) model adjusted by actual stratification factors, the imputed endpoints will be analyzed using each of the 30 datasets. SAS PROC MIANALYZE will be used to generate the final inferences of the risk difference between each risankizumab dose and placebo. Note that measurements will be considered as missing after receiving any antibiotics for HS-related infections or discontinued study drug due to lack of efficacy before MI. Regardless of MI imputed values, subjects receiving any antibiotics for HS-related infections or discontinued study drug due to lack of efficacy will be counted as non-responders at later visits.

Observed Case (OC) analysis will only be performed during the Primary Analysis for the summaries of categorical endpoints for visits after Week 16. The OC analysis will not impute values for missing evaluations, and thus a subject who does not have an evaluation on a scheduled visit will not be included for that visit. The OC analysis will not include values after receiving any prohibited antibiotics for HS-related infections or after discontinued study drug due to lack of efficacy.

9.2.2 Continuous Endpoints

Mixed-Effect Model Repeat Measurement (MMRM) will be the primary approach to handle missing data for continuous endpoints. The MMRM will be conducted using mixed model including observed measurements at all visits, using all available data even if a subject has missing data at some post-baseline visits. The mixed model includes the fixed effects of categorical variables of treatment, actual stratification factors, visit and treatment-by-visit interaction at all post-baseline visits in each Study Period, and the continuous variable of Baseline measurement as covariates. Subjects' observations after receiving any prohibited antibiotics for HS-related infections or discontinued study drug due to lack of efficacy will be excluded from the model. An unstructured variance covariance matrix (UN) will be used. If the model cannot converge, an appropriate covariance structure matrix (e.g., autoregressive (1) or compound symmetry) will be used. The parameter estimations are based on the method of restrictive maximum likelihood (REML). The fixed effects will be used to report model-based means at corresponding visits.

Of note, during the Primary Analysis upon completion of Week 16, the MMRM analysis will only be performed at all visits up to Week 16.

Observed Case (OC) analysis will only be performed during the Primary Analysis for the summaries of continuous endpoints for visits after Week 16. The OC analysis will not impute values for missing evaluations, and thus a subject who does not have an evaluation on a scheduled visit will not be included for that visit. The OC analysis will not include values after receiving any prohibited antibiotics for HS-related infections or after discontinued study drug due to lack of efficacy.

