2.3 Treatment Assignment and Blinding

All subjects will be assigned a unique identification number by the interactive response technology (IRT) system at the screening visit. For subjects who rescreen, the screening number assigned by the IRT at the initial screening visit should be used. The IRT will assign a randomization number that will encode the subject's treatment group assignment according to the randomization schedule generated by the statistics department at AbbVie.

Subjects who meet the study's eligibility criteria will be initially randomized to receive either risankizumab 180 mg or 360 mg as an SC injection or matching placebo up to Week 16 in a 1:1:1 ratio.

Subjects who have been treated with anti-TNF therapy and had inadequate response to this therapy (TNF- IR) will be eligible. Subjects will be randomized by their anti-TNF use (yes or no) prior to Baseline. TNF-naïve (no) subjects will be further stratified by the worst Hurley stage across all affected anatomic regions. Therefore, there will be 4 strata in total:

- Prior exposure to anti-TNF (yes)
- Prior exposure to anti-TNF (no) with the worst Hurley Stage as I
- Prior exposure to anti-TNF (no) with the worst Hurley Stage as II
- Prior exposure to anti-TNF (no) with the worst Hurley Stage as III

All AbbVie personnel of the study (with the exception of AbbVie Drug Supply Management Team) will remain blinded until the Primary Analysis at Week 16 is available. The investigator, study site personnel, and the subject will remain blinded to each subject's initial treatment throughout the study. To maintain the blind, the risankizumab kits and placebo kits provided for the study will be identical in appearance. The IRT will provide access to unblinded subject treatment information in the case of a medical emergency.

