2.4 Sample Size Determination

Under the study design with a 1:1:1 randomization, with the assumed Week 16 HiSCR response rate as summarized in Table 1, a total sample size of 222 subjects will provide 80% to 90% power to detect at least one risankizumab dose is different from placebo (with a 2-sided significance level of 0.025 for the test of each risankizumab dose versus placebo).

Table 1. Power under a 1:1:1 randomization

	Assumed HiSCR Rate at Week 16 (%)			
Assumed Dose Response Model	Placebo (N = 74)	Risankizumab 180 mg (N = 74)	Risankizumab 360 mg (N = 74)	Power ¹
Linear	26%	39.5%	53%	83.9%
EMax	26%	46.5%	53%	87.6%
EMax (with early plateau)	26%	50%	53%	90.6%

^{1.} Power to detect at least one risankizumab dose is different from placebo, under a 2-sided significance level of 0.025 for each risankizumab dose.

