3.2 Secondary Endpoint

The following ranked secondary endpoints will be evaluated at the time points listed:

- Proportion of subjects achieving at least 30% reduction and at least 1 unit reduction from Baseline in Numerical Rating Scale (NRS30) in Patient's Global Assessment of Skin Pain (PGA Skin Pain) at Week 8 among subjects with Baseline Numerical Rating Scale (NRS) ≥ 3. NRS30 is based on worst skin pain in a 24-hour recall period (maximal daily pain).
- 2. Proportion of subjects achieving NRS30 in PGA Skin Pain at Week 16 among subjects with Baseline NRS ≥ 3.
- 3. Proportion of subjects who experience flare, defined as an increase in AN count of at least a 25% with a minimum increase of 2 relative to Baseline (flare), during Period A.
- 4. Change from Baseline in DLQI at Week 16.

- 5. Change from Baseline in HS-related swelling assessed based on the HSSA at Week 16.
- 6. Change from Baseline in HS-related odor assessed based on the HSSA at Week 16.
- 7. Change from Baseline in HS-related worst drainage assessed based on the HSSA at Week 16.

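### Ranked endpoints 5 to 7: a single Baseline slope across visits may cost some Week 16 precision, and the covariance fallback is left open to equal-variance structures

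*SAP*

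**What the plan says.** SAP 9.2.2 models continuous endpoints with treatment, actual stratification factors, visit and treatment-by-visit as categorical effects, plus "the continuous variable of Baseline measurement as covariates". SAP 9.1 gives the same model, "adjusting for the fixed effects of treatment, actual values of stratification factors, visit and treatment-by-visit interaction as covariates", with the Baseline value included. Sections 9.4.2 and 9.5 repeat it. None of the four sections lists a Baseline-by-visit term.

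An unstructured covariance is the first choice, fitted by REML. Only if that model cannot converge does the SAP say that "an appropriate covariance structure matrix (e.g., autoregressive (1) or compound symmetry) will be used". The two structures are examples. No order is fixed, and no heterogeneous-variance option or robust standard error is named.

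The endpoints concerned are the HSSA changes in swelling, odor and drainage, for example "Change from Baseline in HS-related worst drainage assessed based on the HSSA at Week 16" (SAP 3.2). The activity schedule (protocol Appendix D) has HSSA at Weeks 2, 4, 8, 12 and 16 after Baseline in Period A. DLQI is collected only at Week 16 in that period, so neither issue reaches endpoint 4. Each dose is compared with placebo in tests "performed at a two-sided alpha level of 0.025" (SAP 9.1), in the hierarchy of SAP 13.0. SAP 9.4.3 plans no sensitivity analysis for the ranked secondary endpoints.

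**The concern.** There are two separate issues.

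**Precision.** The model lets the treatment effect vary by visit but not the relation between Baseline and change. If that relation differs between Week 2 and Week 16, the fitted slope is a compromise across visits. Week 16, the visit tested, is then adjusted with the wrong slope, and the unexplained part goes into its residual variance. What is at stake is efficiency on three alpha-controlled comparisons per dose.

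**The fallback.** Plain AR(1) and compound symmetry use one variance for all visits. If residual variance grows over time, the pooled variance is too small for Week 16, and so is the model-based standard error. What is at stake is the level of the Week 16 test, but only if the fallback is reached and an equal-variance structure is chosen. Because the list is open, that choice would be made at the analysis stage.

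**Working it through.** **The plan's own figure.** The plan gives no figure for this model. Its stated power, "a total sample size of 222 subjects will provide 80% to 90% power to detect at least one risankizumab dose is different from placebo", concerns HiSCR only. Exact enumeration with Fisher's test at 74 per arm and two-sided 0.025 gives 84.8%, 88.2% and 91.1%, against the stated 83.9%, 87.6% and 90.6%. That is within 1 point, and nothing below alters it.

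**Inputs.** From the documents: 74 per arm, 0.025 two-sided (critical value 2.241), five HSSA visits. Assumed, because the documents give none: Baseline SD 2.2, adjacent-visit residual correlation 0.8, and the visit SDs and Baseline correlations in the table.

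**Formulas.** For visit t with SD s and Baseline correlation r:
- true slope of change on Baseline: β = r × s / 2.2 − 1
- residual variance: R = s² × (1 − r²)
- common slope b: the GLS-weighted mean of the five β, iterated with the unstructured matrix it implies
- Week 16 SE with visit-specific slopes: √[(2/74) × R]
- Week 16 SE with the common slope: √[(2/74) × (R + 2.2² × (β − b)²)]
- actual level when a structure misstates the SE: 2 × [1 − Φ(2.241 × reported SE / true SE)]

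**Worked case (flat SD 2.2, correlation 0.85 falling to 0.3).** R = 4.84 × 0.91 = 4.404. β at Week 16 = −0.70 and b = −0.196. The added term is 4.84 × 0.504² = 1.229. The SE ratio is √(5.634 / 4.404) = 1.131 (0.345 to 0.390), equal to losing about 22% of the sample.

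| Visit SDs, Week 2 to 16 | Baseline correlation | SE increase, unstructured with common slope | AR(1): reported / true SE | AR(1): actual level |
|---|---|---|---|---|
| 2.2, flat | 0.6, constant | 0% | 1.00 | 0.025 |
| 2.2 to 2.8 | 0.7 to 0.5 | 0.1% | 0.83 | 0.06 |
| 2.2, flat | 0.7 to 0.5 | 1.1% | 0.92 | 0.039 |
| 2.4 to 1.9 | 0.7 to 0.5 | 2.1% | 1.02 | 0.022 |
| 2.2 to 2.8 | 0.8 to 0.3 | 5.3% | 0.78 | 0.079 |
| 2.2, flat | 0.85 to 0.3 | 13.1% | 0.82 | 0.065 |

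Compound symmetry behaves almost identically; its highest level is 0.083.

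Two things follow. First, the slope depends on r × s, so rising SDs partly offset a falling correlation, and the largest precision losses need flat SDs. Second, the fallback depends on residual variance. Flat SDs with a falling Baseline correlation still give rising residual variance, hence 0.039 and 0.065 in the flat-SD rows.

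**A second set of assumptions.** Equal SDs, between-visit correlation 0.9 − 0.02 per week apart, Baseline correlation falling from 0.8 to 0.6, 0.5, 0.4 or 0.3: the SE rises by 1.6%, 3.9%, 8.0% or 15.2%. Gentler falls give 0.4% (0.8 to 0.7), 1.2% (0.7 to 0.5) and 0.2% (0.6 to 0.5). If visit SDs also rise 1.33-fold, the four main cases shrink to about 0 to 7%.

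**Fallback by pooled variance alone.** If the SD of change grows from 1.8 to 2.4 in proportion to weeks, the root-mean-square SD is 0.869 of the Week 16 SD, and the level is 2 × [1 − Φ(1.948)] = 0.051. From 1.5 to 2.5 the ratio is 0.796 and the level is 0.074.

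**Simulation.** There were 300 trials in each of four scenarios, with 222 subjects and about 13% dropout depending on the last observed change.
- The unstructured model converged in all 1,200 trials, with a common slope and with Baseline-by-visit.
- Its rejection rate ranged from 1.3% to 4.3%. The Monte Carlo error is √(0.025 × 0.975 / 300), or 0.9 points, so this is only a rough check on the nominal level.
- With SD 2.2 to 2.8 and correlation 0.7 to 0.5, the common-slope mean SE was 0.418 against an empirical SD of 0.400. AR(1) and compound symmetry reported 0.346 and 0.342 against about 0.40, and rejected 5.3% and 5.7%.
- With correlation 0.8 to 0.3, Baseline-by-visit cut the mean SE from 0.483 to 0.458, and the two fallbacks rejected about 11%.
- With SD falling from 2.4 to 1.9, both fallbacks rejected 2.7%.

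**The case against.** A common Baseline slope is a legitimate pre-specified model. Under the unstructured matrix it is also an honest one, because the Week 16 variance absorbs the slope misfit and the reported SE matches the true one in large samples. A reader might infer that the common slope itself understates the standard error. It does not; that risk belongs to the fallback alone.

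A reader might also infer that the plan uses AR(1) or compound symmetry. The SAP puts the unstructured matrix first and moves on only after non-convergence, which did not occur in the simulated trials. Even then the structure must be appropriate, and the two named are examples, so heterogeneous structures are not excluded. With constant or falling residual variance the fallback holds its level.

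Nor do the documents show that the Baseline relation drifts. Entry sets no HSSA threshold, and HSSA Baseline is a weekly average of daily scores (SAP 9.1), which reduces measurement error and so limits regression to the mean. Finally, endpoints 5 to 7 are tested for a dose only after the primary and four ranked endpoints have succeeded.

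All of this stands, and it makes the point minor. It does not remove the case for the change. The extra term costs almost nothing if the slope is stable and recovers precision if it is not. The two structures that the SAP names are ones that can fail when residual variance rises.

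**Conclusion.** The point holds as a minor specification gap in two parts.

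- **Planned model.** The test is valid, with a possible loss of Week 16 precision: 0% with a stable slope, about 0 to 4% of the SE with moderate drift, and 13 to 15% only with a steep fall in Baseline correlation and flat SDs.
- **Fallback.** The nominal 0.025 may become about 0.04 to 0.08. This needs three things together: non-convergence, an equal-variance choice, and residual variance that rises over visits. Otherwise the level is about 0.022 to 0.025. These are levels of a single test, not trial-wide error rates.

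The precision figures and the fallback figures should not be added: the largest precision losses assume flat SDs, while the highest fallback levels come with rising ones. Every size rests on the assumed SDs and correlations. The convergence result comes from simulated normal data fitted by an EM algorithm, so it indicates but does not prove that the planned SAS fit will converge. DLQI, HiSCR and the stated power are unaffected.

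**What to change.** Add a Baseline-by-visit interaction to the MMRM in SAP 9.1, 9.2.2, 9.4.2 and 9.5. In 9.2.2, replace the open examples with a fixed order to follow if the unstructured model does not converge: heterogeneous Toeplitz, then heterogeneous compound symmetry. Use empirical (sandwich) standard errors for the fallback fits only.

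For HSSA this replaces one slope by five, so it uses 4 degrees of freedom among about 220 subjects, plus one SAP sentence for the fallback. It does not change sample size, data collection, the testing hierarchy or the primary analysis. Label: free improvement.
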